### 9.1.2 Cohort design

To characterize the risk factors, clinical course and outcomes for severe disease, a cohort of myocarditis and pericarditis cases (with and without prior exposure to the Moderna vaccine targeting SARS-CoV-2) will be studied. This set will be used for the second primary objective and both secondary objectives.

For the cohort design, eligible cases of myocarditis and pericarditis will be described in terms of demographic characteristics, medical history and vaccination history. The clinical course and long-term outcomes including sequelae will be described and quantified.

## 9.2 Setting

This study will include information from multiple databases, utilizing routinely collected health and administrative data of four European countries: Denmark, Norway, Spain (2 databases), and the United Kingdom (UK). The study databases are representative of the source population in each country (see [Annex 3](#) for details). Both the case-cohort design and the cohort design will draw on data from all five databases.

Briefly, in Denmark and Norway, the registries have full population coverage with respect to the available routinely collected data. The regional databases in Spain (SIDIAP and FISABIO) are representative with respect to background rates and demographic distributions of the underlying regional populations (Catalonia and Valencia, respectively). The CPRD is broadly representative of the UK population.

### 9.2.1 Study period

Recipients of Moderna vaccination targeting SARS-CoV-2 (regardless of age) will be identified starting 06 January 2021 (date of the earliest approval of Moderna vaccination targeting SARS-CoV-2 in Europe). The data on which the full analytical dataset will be available (End of Data collection) is 31 August 2024. Prior to the full analytical dataset being available and cases being identified, data will require extraction, transformation, and quality checks by each of the participating DAPs. In each country, the observation will start on the date of country-specific availability of the Moderna vaccine targeting SARS-CoV-2.

### 9.2.2 Inclusion criteria

For the Moderna vaccination targeting SARS-CoV-2-exposed case-cohort design, a cohort will first be defined including individuals of all ages with (1) at least one dose of Moderna vaccination targeting SARS-CoV-2 administered during the study period, (2) at least one year of enrolment in the applicable database prior to the index vaccine dose to allow for ascertainment of baseline covariables and potential risk factors, and (3) no myocarditis or pericarditis events within 6 months prior to Moderna vaccination receipt. Myocarditis and pericarditis cases are defined when adjudication criteria according to the Brighton Collaboration Case Definition for possible, probable or definite myocarditis or pericarditis is fulfilled. Cases and controls are defined as mentioned in [Section 9.1.1](#).

In the cohort design, all cases following vaccination, and only a sample of cases not following vaccination will undergo adjudication. In the analyses, individuals will be included if they: (1) have been adjudicated and meet the adjudication criteria according to the Brighton Collaboration Case Definition for possible, probable or definite myocarditis or pericarditis, and (2) have at least one year of enrolment in the applicable database prior to the index myocarditis or pericarditis event to allow for ascertainment of baseline covariates and potential risk factors.

For both the case-cohort as the cohort design, individuals with administrative codes for myocarditis or pericarditis will be identified in each data source. Following this initial screening, selected cases will be confirmed based on review of clinical data (based on criteria according to the Brighton Collaboration). The selection will include all cases of myocarditis and pericarditis following Moderna vaccination targeting SARS-CoV-2, as well as an age- and sex- matched sub-sample of other cases.

### **9.2.3 Exclusion criteria**

Individuals not meeting criteria outlined in [Section 9.2.2](#) are excluded from the Moderna vaccination targeting SARS-CoV-2-exposed case-cohort and myocarditis/pericarditis cohort analyses, respectively. For the cohort design an additional exclusion criterium is applied: Persons with no record of a Moderna vaccine targeting SARS-CoV-2 but record of another vaccine for SARS-CoV-2 within 30 days prior to index date of myocarditis or pericarditis event will be excluded. Individuals who have evidence of myocarditis or pericarditis in structured data (e.g., ICD-10 codes) where review of clinical data is not performed due to sampling, or is incompatible with adjudication criteria according to the Brighton Collaboration Case Definition for myocarditis or pericarditis will be described but will not be included as cases in primary analyses. In the Moderna vaccination targeting SARS-CoV-2-exposed case-cohort design, non-confirmed myocarditis/pericarditis cases will be censored at the onset of the false positive myocarditis/pericarditis diagnosis.

## **9.3 Variables**

Availability and definition of specific variables varies by data source, and full information will be sought in collaboration with the DAPs where possible. All data-source specific variable definitions and country-specific data availability will be specified in the SAP.

### **9.3.1 Exposure**

In the Moderna vaccination targeting SARS-CoV-2-exposed case-cohort analysis, multiple risk factors are considered as exposures of interest. In the cohort analysis, multiple prognostic factors are also considered as exposures of interest. See [Section 9.3.3](#) for further details.

In both the Moderna vaccination targeting SARS-CoV-2-exposed case-cohort analysis and the cohort analysis, myocarditis and pericarditis cases will be described as recently-exposed if at least one dose of Moderna vaccination targeting SARS-CoV-2 was received within 30 days prior to the onset of myocarditis/pericarditis. Individuals with exposure more than 30 days prior to onset of myocarditis will be considered to have past exposure, and individuals with no history of Moderna vaccination targeting SARS-CoV-2 will be considered unexposed.

For both Moderna and other vaccinations targeting SARS-CoV-2, it is possible to ascertain the vaccine brand and/or applicable vaccine characteristics from the available data. Exposure to each dose in the order received (e.g., first dose, second dose, booster dose) or any dose of Moderna

vaccination targeting SARS-CoV-2 will be considered. Characteristics of vaccination will also be explored as feasible based on available sample size, including but not limited to dosing interval, dose number, primary series vs booster dose, homologous vs. heterologous schedule, and co-administration with other vaccines.

### 9.3.2 Outcomes

The primary outcome of the Moderna vaccination targeting SARS-CoV-2-exposed case-cohort is myocarditis and pericarditis, which will be analysed combined and separately. For individuals with diagnosis codes for myocarditis/pericarditis within 30 days of exposure, medical records will be reviewed to verify whether they comply with adjudication criteria according to the Brighton Collaboration Case Definition for possible, probable and definite cases.

The cohort analysis of myocarditis and pericarditis cases will include several clinical outcomes such as the hospital readmission and mortality (see [Table 1](#) for details). Outcomes measured will include major adverse clinical outcomes, structural or functional cardiac abnormalities, and patient reported outcomes and functional assessments. Required medication or related cardiac procedures during and following hospitalization, and cardiac or other hospitalization events will be described across the follow-up period. Presence and findings from ambulatory monitoring will also be described during the follow-up period.

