### **8.2 Secondary objectives**

1. To identify whether there are differences in the clinical course and risk factors between myocarditis and pericarditis associated with Moderna vaccination targeting SARS-CoV-2, and myocarditis and pericarditis not associated with vaccinations targeting SARS-CoV-2
2. If severe cases or cases with sequelae are identified, to identify risk factors for severe myocarditis and pericarditis associated with Moderna vaccination targeting SARS-CoV-2

Confirmed cases are those that meet clinical adjudication criteria for myocarditis or pericarditis based on review of clinical data. The adjudication process will use a structured questionnaire that adapts the Brighton Collaboration Case Definition to those elements available in the clinical data available for validation, and will be both informed by expert cardiologist advice and documented in a separate medical record adjudication plan prior to the initiation of case review. Within the cohort study, not all cases undergo validation. All cases following vaccination are included in the validation process, as well as a 1:1 age and sex matched sample of cases not following vaccination.

Final definitions of the level of data details, study variables and detailed descriptions of analyses methods and presentations will be provided in the Statistical Analysis Plan (SAP), which will be developed with clinical and statistical input from all relevant parties involved and the participating database experts.

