**Table 1 Study objectives and endpoints**

Objective	Endpoint	Analysis Set
Primary		
To identify possible risk factors for myocarditis and pericarditis post-Moderna vaccination targeting SARS-CoV-2, including demographic characteristics, medical history, and vaccination characteristics.	Myocarditis or pericarditis within 30 days after Moderna vaccination targeting SARS-CoV-2.	Case-cohort
To characterize the clinical course of myocarditis and pericarditis of varying origin, including myocarditis and pericarditis associated with Moderna vaccination targeting SARS-CoV-2, and myocarditis or pericarditis not associated with vaccinations targeting SARS-CoV-2, and to identify prognostic factors in the course of myocarditis and pericarditis.	Clinical outcomes within 30 days of myocarditis' or pericarditis' onset: 
 
• Acute coronary syndrome or acute myocardial infarction;
 
• Heart failure;
 
• Atrial fibrillation/flutter;
 
• Ventricular arrhythmias/cardiac arrest;
 
• Pulmonary embolism or deep venous thrombosis;
 
	Cohort

	
 
• Stroke outcomes;
 
• Peripheral arterial embolism;
 
• Hospital readmission;
 
• ICU admission; and/or
 
• Death.
 
 
Long term outcome (e.g., 90 day, 6 months or 12 months depending on availability of data):
 
 
• Acute coronary syndrome or acute myocardial infarction;
 
• Heart failure;
 
• Atrial fibrillation/flutter;
 
• Ventricular arrhythmias/cardiac arrest;
 
• Pulmonary embolism or deep venous thrombosis;
 
• Stroke outcomes;
 
• Peripheral arterial embolism;
 
• Hospital readmission;
 
• ICU admission; and/or.
 
• Death.
 
	

Secondary
		

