### 9.7.5 Sensitivity analyses

Sensitivity analysis will focus on the robustness of results regarding assumptions of the study design, outcome definitions, assumed period of risk, and availability of key data elements and may include the following (as feasible based on available sample size within the applicable subgroups):

- The exposure window for recent exposure to Moderna vaccination targeting SARS-CoV-2 prior to myocarditis/pericarditis events will be shortened from 30 days to 7 days and 14 days.
- The myocarditis/pericarditis case definition may be modified to include (1) validated cases classified as Definitive or Probable (Level 1-2) for a restricted sensitivity analysis, or classified as Definitive, Probable, Possible, or Insufficient Information (Levels 1-4) for an expanded sensitivity analysis, by adjudication criteria according to the Brighton Collaboration Case Definition, or (2) all cases (including validated and unvalidated cases) .
- If a large number of individuals with a history of myocarditis/pericarditis are identified, these individuals may be excluded in sensitivity analyses.

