- The GAIA Pharmaceutical module stores data on all outpatient pharmaceutical prescriptions and dispensings, including both primary care and outpatient hospital departments, using the Anatomical Therapeutic Chemical (ATC) classification system and the National Pharmaceutical Catalogue, which allow the identification of the exact content of each dispensing. GAIA does not include in-hospital medication or medication administered in the Accident and Emergency Department (AED). GAIA provides detailed information on prescriptions issued by physicians, such as the duration of treatment and dosage.
- The Hospital Medical Record (ORION) provides comprehensive information covering all areas of specialised care, from admission, outpatient consultations, hospitalisation, emergencies, diagnostic services (e.g., laboratory tests, imaging, microbiology, pathology), pharmacy, surgical block including day surgery, critical care, prevention and safety, social work, at home hospitalisation, and day hospitalisation. ORION is currently in the process of being integrated for the whole region, with several databases already fully integrated and available for all hospitals, including the Minimum Basic Data Set at Hospital Discharge (MBDS) and the AED clinical record.
- The MBDS is a synopsis of clinical and administrative information on all hospital admissions and major ambulatory surgery in the Valencia health system hospitals, including public-private partnership hospitals (approximately 450,000 admissions per year in the region). The MBDS includes admission and discharge dates, age, sex, geographic area and zone of residence, main diagnosis at discharge, up to 30 secondary diagnoses (comorbidities or complications), clinical procedures performed during the hospital episode, and the diagnosis-related group(s) assigned at discharge. The MBDS used the ICD-

9-CM system for coding through December 2015 and ICD-10-ES afterward. The MBDS was extended in 2015 to include the “present on admission” diagnosis marker and information on tumour morphology.

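### Section 9.3.2 selects records for review by a diagnosis code within 30 days of exposure, but recent exposure is counted from onset and other sections set no such code limit

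*Protocol*

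**What the plan says.** The protocol describes in several places which cases are reviewed or counted, and by which date.

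- Section 9.3.2 (Outcomes), case-cohort: "For individuals with diagnosis codes for myocarditis/pericarditis within 30 days of exposure, medical records will be reviewed". The trigger is the date of a code.
- Section 9.3.1 (Exposure), both designs: a case is recently exposed "if at least one dose of Moderna vaccination targeting SARS-CoV-2 was received within 30 days prior to the onset of myocarditis/pericarditis". The anchor is onset.
- Table 1, primary objective 1: "Myocarditis or pericarditis within 30 days after Moderna vaccination targeting SARS-CoV-2". The date that decides this is not named.
- Section 9.2.2 (Inclusion criteria), both designs: "The selection will include all cases of myocarditis and pericarditis following Moderna vaccination targeting SARS-CoV-2". There is no 30-day limit.
- Section 8.2, on the cohort study: "All cases following vaccination are included in the validation process". Again there is no limit.
- Section 9.1.1 takes as cases those who develop the disease at any time during follow-up.
- Section 9.7.5: the recent-exposure window "will be shortened from 30 days to 7 days and 14 days".

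Section 9.2.2 makes fulfilled Brighton adjudication criteria a condition for being a case. An event that is not reviewed therefore cannot be a primary case. The protocol does not say whether onset means first symptoms, the code date or a date found at adjudication.

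**The concern.** A code is recorded at or after the health-care contact that produces it, so it normally follows onset. Section 9.3.2 gives the code the same 30 days that Section 9.3.1 gives onset, with no margin. A person with onset on day 27 and a code on day 34 is recently exposed under Section 9.3.1, is reviewed under Section 9.2.2, and is not selected under Section 9.3.2. The reverse can also occur: symptoms that began before vaccination but were coded after it pass the code trigger, and the protocol does not say how an adjudicated onset before vaccination is classified.

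Two things are at stake. Primary objective 1 rests on few cases (Section 9.5 expects 20 to 80 myocarditis cases per data access provider), so avoidable losses matter. The models are also fitted locally at five providers (Section 9.7.2), and rules that conflict on who is reviewed can be applied differently from one provider to the next.

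**Working it through.** **The plan's own figures.** Section 9.5 derives 27 to 274 myocarditis cases from Table 3. The recipients sum to 675,345 + 1,646,900 + 1,386,090 + 3,107,305 + 28,536 = 6,844,176. Multiplied by 0.4 and 4.0 per 100,000 this gives 27.4 and 273.8, so the figure reproduces. Five providers times 20 to 80 gives 100 to 400, which also reproduces. Neither figure depends on the review trigger.

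**Inputs that must be assumed.** The protocol gives no distribution for the time to onset or for the delay from onset to code.

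- Delay: exponential with mean m of 3 or 7 days.
- Onset, front-loaded: exponential with scale a = 7 days, truncated at day 30. This puts (1 − e^(−2))/(1 − e^(−30/7)) = 0.865/0.986 = 88% of onsets within 14 days, in line with Section 7, where cases arose mainly within 14 days.
- Onset, uniform over days 0 to 30: a pessimistic contrast that does not fit Section 7.

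**Formula.** For cases with onset at or before day W, the share coded after day 30 is the integral over t from 0 to W of f(t)·e^(−(30−t)/m), where f is the onset density given onset by W. The trigger stays at day 30 for every W, because that is the only code limit the protocol states.

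- Uniform onset: (m/W)·(e^(−(30−W)/m) − e^(−30/m)). For W = 30, m = 3: 0.1 × (1 − e^(−10)) = 10.0%. For W = 30, m = 7: 0.2333 × (1 − 0.0138) = 23.0%. For W = 14, m = 7: 0.5 × (0.1017 − 0.0138) = 4.4%. For W = 7, m = 7: 0.0374 − 0.0138 = 2.4%.
- Front-loaded onset with a = m = 7: e^(−30/7)·(W/7)/(1 − e^(−W/7)). For W = 30: 0.01376 × 4.286/0.9862 = 6.0%. For W = 14: 0.01376 × 2/0.8647 = 3.2%. For W = 7: 0.01376/0.6321 = 2.2%.
- Front-loaded onset with m = 3, integrated numerically: 1.0%, 0.05% and 0.01% for W = 30, 14 and 7.

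| Onset window | Front-loaded, mean delay 3 to 7 days | Uniform, mean delay 3 to 7 days |
|---|---|---|
| 30 days | 1.0% to 6.0% | 10.0% to 23.0% |
| 14 days | 0.05% to 3.2% | 0.1% to 4.4% |
| 7 days | 0.01% to 2.2% | 0.02% to 2.4% |

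The short windows lose least because a case with onset by day 14 has at least 30 − 14 = 16 days to be coded in time, and one with onset by day 7 has at least 30 − 7 = 23.

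**In cases.** As an illustration only, 1% to 6% of 100 to 400 onset-eligible myocarditis cases is 0.01 × 100 = 1 to 0.06 × 400 = 24 cases across the five providers.

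**With the Section 9.2.2 selection.** Without the 30-day code limit, this loss is zero by construction.

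**The case against.** The strongest reply is that Sections 8.2 and 9.2.2 already send every post-vaccination case to review. Section 9.3.2 does not say that later codes are left out, and the only reason Section 9.2.3 gives for not reviewing a record is sampling, which applies to cases not following vaccination. This stands to the extent that a reader who infers that late-coded cases are never reviewed goes too far. What remains is a conflict between stated rules, one of which loses cases if it is followed.

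It can also be said that details of dating belong in the SAP or in the separate adjudication plan. That is fair for source-specific definitions, but neither document can carry out protocol sections that disagree on who is reviewed.

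Four stronger readings are tempting and are not supported:

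- That the 7- and 14-day analyses lose many true cases. Under the same delay assumptions, losses of 11% to 63% appear only if those windows are cut on the code date. Section 9.7.5 shortens the exposure window before the event and sets no code deadline at day 7 or 14.
- That the odds ratios are inflated. This needs a delay that differs between risk-factor groups, and nothing in the protocol documents one.
- That the Valencia hospital data prove a delay because they hold the "main diagnosis at discharge, up to 30 secondary diagnoses". The same sentence in Annex 3 lists admission dates, and the annex also describes a present-on-admission marker and emergency records.
- That onset before vaccination enters as post-vaccine disease. Records are adjudicated, and Section 9.2.2 excludes people with an event in the 6 months before vaccination. The protocol leaves the classification unstated; it does not state a wrong one.

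**Conclusion.** The point holds as an internal conflict with a modest, avoidable loss of cases. Section 9.3.2 triggers review on a code date, Section 9.3.1 counts from onset, and Sections 8.2, 9.1.1 and 9.2.2 have no 30-day code limit. If Section 9.3.2 governs, the 30-day primary case set loses about 1% to 6% of onset-eligible cases with front-loaded onset. The 10% to 23% under uniform onset is an upper contrast that fits the protocol's background poorly. Both ranges rest on an assumed exponential delay with a mean of 3 to 7 days, and longer delays would raise them. Under the same assumptions the 14- and 7-day analyses lose at most 4.4% and 2.4%. Table 1 does not itself use the word onset, so the mismatch is with the exposure definition and the other selection rules, not with the endpoint row alone. The correction should be made because it is specific and cheap.

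**What to change.** 1. In Section 9.3.2, replace the 30-day code trigger with the selection in Section 9.2.2 (all codes after Moderna vaccination), or at least allow a stated margin beyond day 30.
2. Reconcile Sections 8.2, 9.1.1, 9.2.2 and 9.3.2 and Table 1, so that a single rule says which post-vaccination codes are reviewed and which confirmed cases count for the 30-day endpoint.
3. Define onset once. State in Sections 9.3.1 and 9.7.5 that the adjudicated onset date sets case status, recent or past exposure, and the 30-, 14- and 7-day windows.
4. State that a case whose adjudicated onset precedes vaccination is not a post-vaccine case.
5. Restrict code dates to the sensitivity analysis that includes unvalidated cases.

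The cost is wording in these sections and the review of some records coded after day 30. Section 9.2.2 already implies that review, so it adds little to the planned work.

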**Table 1 Study objectives and endpoints**

Objective	Endpoint	Analysis Set
Primary		
To identify possible risk factors for myocarditis and pericarditis post-Moderna vaccination targeting SARS-CoV-2, including demographic characteristics, medical history, and vaccination characteristics.	Myocarditis or pericarditis within 30 days after Moderna vaccination targeting SARS-CoV-2.	Case-cohort
To characterize the clinical course of myocarditis and pericarditis of varying origin, including myocarditis and pericarditis associated with Moderna vaccination targeting SARS-CoV-2, and myocarditis or pericarditis not associated with vaccinations targeting SARS-CoV-2, and to identify prognostic factors in the course of myocarditis and pericarditis.	Clinical outcomes within 30 days of myocarditis' or pericarditis' onset: 
 
• Acute coronary syndrome or acute myocardial infarction;
 
• Heart failure;
 
• Atrial fibrillation/flutter;
 
• Ventricular arrhythmias/cardiac arrest;
 
• Pulmonary embolism or deep venous thrombosis;
 
	Cohort

	
 
• Stroke outcomes;
 
• Peripheral arterial embolism;
 
• Hospital readmission;
 
• ICU admission; and/or
 
• Death.
 
 
Long term outcome (e.g., 90 day, 6 months or 12 months depending on availability of data):
 
 
• Acute coronary syndrome or acute myocardial infarction;
 
• Heart failure;
 
• Atrial fibrillation/flutter;
 
• Ventricular arrhythmias/cardiac arrest;
 
• Pulmonary embolism or deep venous thrombosis;
 
• Stroke outcomes;
 
• Peripheral arterial embolism;
 
• Hospital readmission;
 
• ICU admission; and/or.
 
• Death.
 
	

Secondary
		

To identify whether there are differences in the clinical course and risk factors between myocarditis and pericarditis associated with Moderna vaccination targeting SARS-CoV-2, and myocarditis and pericarditis not associated with vaccinations targeting SARS-CoV-2.
	
Clinical outcomes within 30 days of myocarditis' or pericarditis' onset:
 
 
• Acute coronary syndrome or acute myocardial infarction
 
• Heart failure
 
• Atrial fibrillation/flutter
 
• Ventricular arrhythmias/cardiac arrest
 
• Pulmonary embolism or deep venous thrombosis
 
• Stroke outcomes
 
• peripheral arterial embolism
 
• Hospital readmission
 
• ICU admission
 
• Death
 
	
Cohort

	
Long term outcome (90 day, 6 months or 12 months depending on availability of data):
 
 
• Acute coronary syndrome or acute myocardial infarction;
 
• Heart failure;
 
• Atrial fibrillation/flutter;
 
• Ventricular arrhythmias/cardiac arrest;
 
• Pulmonary embolism or deep venous thrombosis;
 
• Stroke outcomes;
 
• Peripheral arterial embolism;
 
• Hospital readmission;
 
• ICU admission; and/or
 
• Death.
 
	

If severe cases or cases with sequelae are identified, to identify risk factors for severe myocarditis and pericarditis associated with Moderna vaccination targeting SARS-CoV-2.
	
Severe myocarditis or pericarditis within 30 days after Moderna vaccination targeting SARS-CoV-2, as well as severe myocarditis or pericarditis in the longer term.
	
Cohort

Additionally, the acute phase of care for the initial myocarditis episode will be described with respect to the following characteristics:

- Highest level of care (outpatient, emergency department visit, inpatient, intensive care unit)
- Length of stay in the hospital

